#### **9.4.4 Safety Analyses**

To assess severe adverse events (SAEs), we will consider otic barotrauma, myopia, oxygen toxicity seizures and acute pulmonary edema. For each patient we will count the total number of SAEs during hospitalization.

SAEs will be summarized by computing mean and standard deviation for each comparison group. We will further compare mean number of SAEs between HBOT and SOC groups using linear regression. The outcome will be log transformed to account for the potential violation of normality. We will report difference in mean along with 95% confidence interval around the mean.

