## List of Abbreviations

AE	Adverse Event/Adverse Experience
CFR	Code of Federal Regulations
CRF	Case Report Form
CSOC	Clinical Study Oversight Committee
DCC	Data Coordinating Center
DHHS	Department of Health and Human Services
DSMB	Data and Safety Monitoring Board
FFR	Federal Financial Report
FWA	Federalwide Assurance
GCP	Good Clinical Practice
HIPAA	Health Insurance Portability and Accountability Act
ICF	Informed Consent Form
ICH	International Conference on Harmonisation
IRB	Institutional Review Board
ISM	Independent Safety Monitor
MOP	Manual of Procedures
N	Number (typically refers to participants)
NIH	National Institutes of Health
OHRP	Office for Human Research Protections
OHSR	Office of Human Subjects Research
PI	Principal Investigator
QA	Quality Assurance
QC	Quality Control
SAE	Serious Adverse Event/Serious Adverse Experience
SOP	Standard Operating Procedure
US	United States
HBOT	Hyperbaric Oxygen Therapy
COVID-19	2019 Novel Coronavirus

CONFIDENTIAL

This material is the property of the NYU School of Medicine and Langone Medical Center. Do not disclose or use except as authorized in writing by the study sponsor  
Interventional Template Version: 11 January 2019

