Objectives	Determine Safety and Efficacy of Hyperbaric Oxygen as an adjunctive treatment for COVID 19 hospitalized patients
Methodology	This is a prospective interventional cohort study that will evaluate the risks and benefits of HBOT utilization for COVID-19 confirmed patients in the hospital setting.
Endpoint	Primary endpoint: Death Secondary endpoints: Need for invasive mechanical ventilation, reduction in days on a ventilator Safety endpoints: Incidence of adverse events (AE) and severe adverse events (SAE)
Study Duration	Approximately two months, but subject to change given the nature of the ongoing pandemic.
Participant Duration	Duration of inpatient hospitalization.
Intervention	Up to 5 hyperbaric oxygen treatments at 2.0 ATA for 90 minutes dependent on the ability of the patient to participate
Population	Patients greater than 18 years of age diagnosed with COVID19 and under respiratory distress.

CONFIDENTIAL

This material is the property of the NYU School of Medicine and Langone Medical Center. Do not disclose or use except as authorized in writing by the study sponsor

Eligibility Criteria	
Inclusion criteria:
 
 
1. Laboratory confirmed COVID-19 positive or a clear clinical diagnosis of COVID-19
 
2. SpO2 <93% after trial of non-rebreather with no less than 85% SpO2
 
3. At least 18 years of age
 
4. No absolute contraindication for Hyperbaric Oxygen
 
 
Exclusion criteria:
 
 
1. Pregnancy
 
2. Untreated Pneumothorax
 

Study Sites	
NYU Winthrop Hospital          NYU Langone School of Medicine          Northwell Hospital          Cleveland Clinic          Loma Linda          Jacobi/Einstein          University of Kentucky Hospital          Westchester Medical Center          Geisinger Commonwealth School of Medicine          Spectrum Health Hospital          University of Illinois at Urbana-Champaign

Number of participants	
40 patients in severe respiratory distress          (SpO2 < 93% on RA, but oxygen responsive)

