### 8.3 Definition of Serious Adverse Events (SAE)

#### Serious Adverse Event

Adverse events are classified as serious or non-serious. A **serious adverse event** is any AE that is:

- fatal
- life-threatening
- requires or prolongs hospital stay
- results in persistent or significant disability or incapacity
- a congenital anomaly or birth defect
- an important medical event

Important medical events are those that may not be immediately life threatening, but are clearly of major clinical significance. They may jeopardize the subject, and may require intervention to prevent one of the other serious outcomes noted above. For example, drug overdose or abuse, a seizure that did not result in in-patient hospitalization, or intensive treatment of bronchospasm in an emergency department would typically be considered serious.

All adverse events that do not meet any of the criteria for serious should be regarded as **non-serious adverse events**.

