### 9.2 Statistical Hypotheses

For primary endpoint: we hypothesize that the proportion of patients who died in the HBOT group will be lower than that in the SOC group. We will test the hypothesis against the null of no difference in proportions of incident mortality.

For secondary end points:

1. We hypothesize that the proportion of patient who need mechanical ventilation in the HBOT group will be lower than that in the SOC group. We will test the hypothesis against the null of no difference in proportions between the two groups.
2. We further hypothesize that the patients in the HBOT group will spend on average fewer number of days on a ventilator compared to those in the SOC group. We will test the hypothesis against the null that there is no difference in means between the two groups.

Safety analysis: We hypothesize that the rate of any severe adverse effects will be smaller in the HBOT group compared to the SOC group. We will test the hypothesis against the null of no difference.

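### Section 9.4.4 applies the SAE label to four events that 4.2.3 and 8.1 list as HBOT-related AEs, and log-transforms a per-patient count with no rule for zeros, so the promised difference in mean cannot be obtained as written.

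*Combined protocol and SAP*

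**What the plan says.** **What is counted.** Section 9.4.4 states: "To assess severe adverse events (SAEs), we will consider otic barotrauma, myopia, oxygen toxicity seizures and acute pulmonary edema". The same four events appear in 4.2.3 and 8.1, where they are adverse events possibly related to HBOT. Section 8.3 has no event list. It says "Adverse events are classified as serious or non-serious" and then applies outcome criteria such as fatal, life-threatening or prolonging the hospital stay. The List of Abbreviations expands SAE as "Serious Adverse Event/Serious Adverse Experience". The Protocol Summary nevertheless gives the safety endpoint as "Incidence of adverse events (AE) and severe adverse events (SAE)", and 4.2.3 and 9.4.4 also write *severe*. In 8.5.1 *severe* is a separate grade of intensity. Section 4.2.3 promises per-patient totals of both AEs and SAEs; 9.4.4 analyses one total only.

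**The hypothesis.** Section 9.2 states: "We hypothesize that the rate of any severe adverse effects will be smaller in the HBOT group compared to the SOC group".

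**The model.** In 9.4.4, "SAEs will be summarized by computing mean and standard deviation for each comparison group". The groups are then compared by linear regression on the per-patient count, and "The outcome will be log transformed to account for the potential violation of normality". The promised result is: "We will report difference in mean along with 95% confidence interval around the mean".

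**The concern.** Safety is half of the purpose stated in section 3, and 9.4.4 is where the plan says how SAEs are to be compared between 40 HBOT and 120 standard-of-care (SOC) patients. Two things are unsettled there.

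First, the outcome. An event list and an outcome-based definition select different events, and a reader cannot tell which of them *SAE* means in the results table.

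Second, the estimate. Most patients may have no such event, and the logarithm of zero does not exist. The analyst has to invent a rule, and the reported effect then depends on that rule. Whatever the rule, a log-scale slope is not a difference in mean counts.

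Two analysts who both follow 9.4.4 could therefore count different events and report effects of different size.

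**Working it through.** The documents give no SAE rate, power or precision for safety, so there is no stated figure to reproduce. Group sizes (40 and 120) come from 9.3; the two-sided 0.05 level comes from 9.4.1. All event rates below are assumptions.

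**1. Label.**
- 4.2.3 and 8.1: the four events are HBOT-related AEs. 9.4.4: the same four are the SAEs.
- 8.3: an event is serious by its outcome. A mild otic barotrauma or mild myopia need not qualify, yet 9.4.4 counts it.
- 2.4.1 names pneumothorax as possibly fatal. It is not among the four. Under 4.2.3 and 8.6 it is still recorded, but it does not enter the 9.4.4 count if the list is exclusive.
- 9.2 speaks of a rate of *any* severe effect; 9.4.4 compares a mean count. Scope and measure both differ.

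**2. How likely are zeros?** For a Poisson mean m per patient, P(zero) = exp(−m), and P(no zero among 160) = (1 − exp(−m))^160.

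| m | P(zero) | expected zeros of 160 | P(no zero among 160) |
|---|---|---|---|
| 0.05 | 0.951 | 152 | below 1e-10 |
| 0.5 | 0.607 | 97 | below 1e-10 |
| 1 | 0.368 | 59 | below 1e-10 |
| 3 | 0.050 | 8 | 0.0003 |

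At least one zero is practically certain over this range.

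**3. What does an added constant do?** With log(Y + k) as outcome, the expected slope is E[log(Y + k)] in HBOT minus E[log(Y + k)] in SOC.

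| Means, HBOT v SOC | true difference | k = 1 | k = 0.5 | k = 0.1 | k = 0.01 |
|---|---|---|---|---|---|
| 0.2 v 0.1 | 0.10 | 0.065 | 0.102 | 0.215 | 0.407 |
| 0.6 v 0.8 | −0.20 | −0.106 | −0.155 | −0.295 | −0.519 |

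In the first row the slope varies about sixfold (0.407/0.065 = 6.3). The value at k = 0.5 lies near 0.10 by coincidence; in the second row the same constant gives −0.155 for a true −0.20.

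**4. The log slope is a different quantity even without zeros.** For counts 1, 1, 2, 4 against 1, 2, 2, 3, both means are 2 and the difference is 0. The mean logs are 0.520 and 0.621, so the slope is −0.101.

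**5. Does the test suffer?** Two-sided t-test, 40 v 120, 20,000 simulated trials, run twice. At 0.2 v 0.1, rejection is 33% to 36% over the four constants and 35% to 36% on raw counts. At 0.6 v 0.8 it is 21% to 24%, and 23% on raw counts. The choice of constant hardly matters for the test. Dropping event-free patients does: rejection falls to about 3% (with no test possible in 28% of trials) and to 8%. At 0.2 v 0.1 that would leave about 40 × (1 − exp(−0.2)) = 7 HBOT and 120 × (1 − exp(−0.1)) = 11 SOC patients.

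**6. What the count scale gives.** Assumed data: HBOT 32 patients with 0 events, 6 with 1 and 2 with 2 (mean 10/40 = 0.25); SOC 114 with 0 and 6 with 1 (mean 6/120 = 0.05). The log is undefined for 32 + 114 = 146 of 160 patients. Untransformed regression with robust standard errors gives a difference of 0.20 (95% CI 0.03 to 0.37).

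**The case against.** - **A listed event can be serious.** This stands. Section 8.3 itself uses a seizure as an example of an important medical event, and 2.3 describes pulmonary edema that leads to ventilatory support. A reader might infer that none of the four events is an SAE; the documents do not support that. The conflict lies in identifying SAEs by name, and it is clearest for otic barotrauma and myopia.
- **The list may not be exclusive.** The verb in 9.4.4 is *consider*. If the list is only illustrative, no event is lost, but then 9.4.4 does not say what is counted. A reader might also infer that deaths escape comparison. They do not: death is the primary endpoint and is compared under 9.4.2.
- **This is not the only look at safety.** This stands. Section 9.4.7 plans an interim analysis of all endpoints, 10 HBOT against 30 matched SOC patients, and the investigators review safety data by arm after 10, 20 and 40 patients.
- **The raw means and SDs are reported anyway.** This also stands: a raw difference could be formed from them. But the regression does not estimate it, and no interval method for it is given.
- **A later SAP could supply the zero rule.** Section 9.1 has that SAP written at the end of a non-blinded study, after the interim analysis. The event definition and the constant would be chosen with data in hand. By contrast, 9.4.3 at least makes the log of ventilator days conditional on non-normality; 9.4.4 sets no condition. Neither 9.4.1 nor 9.4.4 mentions zeros.

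**Conclusion.** The point holds as an error of definition and of analysis in 9.4.4, and should be fixed. The label contradicts 4.2.3, 8.1 and 8.3 on the face of the text and needs no assumption. The regression fails once one patient has a zero count. That is practically certain for Poisson means up to 3 per patient, a range assumed because the documents give none. Depending on the constant, the reported effect for a true difference of 0.10 lies anywhere from 0.065 to 0.407.

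The consequence is limited to the size and meaning of the safety estimate. A reader might infer that the safety test is invalid or loses its power. That does not follow: rejection rates hardly move across constants and match those on raw counts, and they collapse only if event-free patients are discarded, which the plan does not propose. Pneumothorax and other unlisted events are still recorded. The primary analysis and the halting rules are not affected.

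**What to change.** 1. In the Protocol Summary, 4.2.3 and 9.4.4, write *serious* and refer to the 8.3 definition. Leave the severity grades in 8.5.1 as they are. The sponsor should state whether the effects named in the 9.2 safety hypothesis are 8.3 SAEs or events of the severe grade in 8.5.1; the text allows either.
2. In 9.4.4, delete the log transform. Name the untransformed difference in mean SAE count per patient, with a robust or bootstrap 95% CI, as the main safety comparison. This delivers what the section already promises.
3. As a supporting summary, report the proportion of patients with at least one SAE, with and without death, with a score or exact 95% CI. The version without death shows what the primary endpoint does not already show.
4. Tabulate the four HBOT-related AEs, plus pneumothorax, separately from SAEs.

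**Cost.** Wording in three places and one clarification in 9.2. Seriousness must be classified for the 120 SOC patients, within the chart review already planned in 5.7. HBOT events are recorded prospectively from consent and SOC events are read from charts, so ascertainment may differ between groups. None of these changes removes that, and the report should say so. Sample size, primary analysis and halting rules stay as they are.

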### **2.3 Rationale**

Covid-19 is a novel respiratory pathogen with alarming rates of transmission and morbidity and mortality. The predominant presentation is URI symptoms that may present as hypoxic respiratory failure without hypercarbia and tachypnea. Patients are then noted to develop acute pulmonary edema requiring ventilatory support. It is thought that an inflammatory cascade leads to increased capillary permeability. Hyperbaric oxygen may have a role if delivered before patients develop respiratory failure thus decreasing the need for ventilators

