### **2.5 Known Potential Benefits**

Hyperbaric Oxygen has the benefit of improving local and systemic tissue hypoxia, reducing edema and may blunt the inflammatory response.

CONFIDENTIAL

This material is the property of the NYU School of Medicine and Langone Medical Center. Do not disclose or use except as authorized in writing by the study sponsor

Interventional Template Version: 11 January 2019

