#### **4.2.3 Safety Endpoints**

We will collect all adverse events (AE), including severe adverse events (SAEs) for the study. For AEs potentially related to HBOT we will consider otic barotrauma, myopia, oxygen toxicity seizures and acute pulmonary edema. For each patient we will count the total number of AEs and SAEs during hospitalization.

CONFIDENTIAL

This material is the property of the NYU School of Medicine and Langone Medical Center. Do not disclose or use except as authorized in writing by the study sponsor

Interventional Template Version: 11 January 2019

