#### **9.4.3 Analysis of the Secondary Endpoint(s)**

The first secondary endpoint is a binary outcome indicating whether a patient needed a mechanical ventilation. We will compute the proportion of patients who needed mechanical ventilation during their treatment for each matched group. The proportion in HBOT arm will be compared with that in matched SOC using chi-square test for proportions. Estimate of difference in proportion along with 95% confidence interval will be reported. Similar to the primary analysis, we will adjust for any potential confounders, deemed important in the baseline analysis, by using multivariable logistic regression. Estimate of odds-ratio and 95% confidence interval will be reported.

To compare the average number of days spent in ventilator between the two groups, we will use linear regression analysis. The distribution of outcome, the number of days in ventilator, will be assessed graphically and by conducting test for normality. If we find the evidence of deviation from normal distribution the outcome will be log transformed before proceeding with analysis. We will also adjust for any potential confounders, deemed important in the baseline analysis. Slope coefficient along with 95% confidence interval will be reported as an estimate of difference between HBOT and SOC groups.

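### Section 9.4.4 adds acute pulmonary edema, a step on the plan's own efficacy pathway, to chamber injuries in one count, so an edema benefit can offset HBOT-specific harm in the planned safety comparison

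*Combined protocol and SAP*

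**What the plan says.** Section 9.4.4 names the events for the safety analysis: "we will consider otic barotrauma, myopia, oxygen toxicity seizures and acute pulmonary edema". It then pools them: "For each patient we will count the total number of SAEs during hospitalization". The mean total is compared between HBOT and SOC by linear regression after a log transformation. Sections 4.2.3 and 8.1 give the same four events under a different label, as adverse events possibly caused by treatment: "For AEs potentially related to HBOT we will consider otic barotrauma, myopia, oxygen toxicity seizures and acute pulmonary edema".

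On the disease course, section 2.3 says: "Patients are then noted to develop acute pulmonary edema requiring ventilatory support". It continues: "Hyperbaric oxygen may have a role if delivered before patients develop respiratory failure thus decreasing the need for ventilators". Section 2.5 lists among the benefits of HBOT "reducing edema and may blunt the inflammatory response". Section 9.4.3 makes ventilation an efficacy outcome: "The first secondary endpoint is a binary outcome indicating whether a patient needed a mechanical ventilation".

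Section 9.2 sets the direction of the safety hypothesis: "We hypothesize that the rate of any severe adverse effects will be smaller in the HBOT group compared to the SOC group". The comparison group is a matched chart-review cohort that received no hyperbaric oxygen (4.2.2, 9.3).

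**The concern.** Three of the four components (otic barotrauma, myopia, oxygen toxicity seizure) come from pressure or high-dose oxygen, so essentially they can only add to the HBOT total. The fourth lies on the path that HBOT is meant to interrupt. One sum therefore carries two signals that may point in opposite directions, and the regression reports only their net.

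Safety is a stated purpose of the study (section 3), and 9.4.4 is the only planned between-group analysis of it. A lower HBOT mean would be taken as support for the 9.2 safety hypothesis, although it could restate an effect on disease progression while chamber injuries occur in the treated group.

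**Working it through.** **Inputs from the plan.** 40 HBOT and 120 SOC patients; two-sided 0.05 (9.4.1, 9.5). Need for ventilation is 80% in SOC (9.4.2), with a detectable difference of 22.5 percentage points (9.5), hence 57.5% in HBOT.

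**Inputs the plan does not give (assumptions).** Edema is recorded in a share q of ventilated patients, with the same q in both groups. A proportion i of HBOT patients has one chamber injury and no SOC patient has any. Edema and injury are independent. The 57.5% is the plan's detectable effect, not a forecast.

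**Step 1: the plan's own power.** Pooled proportion = (40 × 0.575 + 120 × 0.80)/160 = 0.74375. Standard error under the null = √[0.74375 × 0.25625 × (1/40 + 1/120)] = 0.0797. Under the alternative = √[0.575 × 0.425/40 + 0.80 × 0.20/120] = 0.0863. z = (0.225 − 1.96 × 0.0797)/0.0863 = 0.797, which gives power of 78.7% against the stated 80%. The planning figures reproduce closely enough to use.

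**Step 2: break-even in the pooled mean.** Difference in mean count, HBOT minus SOC:

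D = i − q × (0.80 − 0.575) = i − 0.225q

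D is zero at i = 0.225q, that is 40 × 0.225q = 9q injured HBOT patients:

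- q = 1: 9.0 injuries
- q = 0.5: 4.5 injuries
- q = 0.25: 2.25 injuries

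This holds for the raw mean. On log(1 + count), the q = 1 break-even point still shows a difference of about −0.037, slightly in favour of HBOT.

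**Step 3: what the planned test would show.** The 9.4.4 comparison was simulated as a t-test on log(1 + count), 40 v 120, with i = 10%. The last column is Fisher's exact test on chamber events alone against 0/120. It is significant from 3 injured patients upwards, and P(at least 3 of 40 at 10%) = 0.777.

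| Edema SOC / HBOT | Raw D | Pooled: significant for HBOT | Pooled: significant harm | Chamber events alone: harm |
|---|---|---|---|---|
| 80% / 57.5% (q = 1) | −0.125 | about 46% | under 0.1% | 78% |
| 40% / 28.75% (q = 0.5) | −0.0125 | 4 to 5% | 1 to 2% | 78% |
| 20% / 14.4% (q = 0.25) | +0.044 | about 1% | about 8% | 78% |
| 50% / 50% (no benefit) | +0.10 | under 1% | about 14% | 78% |
| 20% / 20% (no benefit) | +0.10 | about 0% | about 23% | 78% |

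With q = 1 and no injuries at all, the pooled test favours HBOT in 78.7% of trials. That equals the power of the ventilation comparison in step 1, so in that limiting case the safety test is the efficacy test under another name.

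**Step 4: the no-benefit case.** With equal edema rates, edema contributes nothing to the expected difference. In the last two rows the harm stays in D (+0.10), but the variance from disease events cuts the chance of showing it from 78% to about 14% or 23%.

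**The case against.** The strongest reply is that nothing is concealed. All adverse events are recorded (4.2.3, 8.6) and graded for causality (8.5.2), and individual data are listed (9.4.10). Seizures are followed as a separate item at 10, 20 and 40 patients (8.12, 9.4.7.1). This stands: a reader might infer that injuries would vanish from the trial, and the documents do not support that. None of these provisions, however, is a planned comparison or summary by event type, and 9.4.4 does not use the causality grade, which in any case has no meaning for SOC patients.

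Second, 4.2.3 and 8.1 list edema as possibly related to HBOT. For an event with two possible causes a comparison with SOC is informative. This also stands, and it is a reason to report edema separately, not to drop it from the safety events.

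Third, a reader might infer that, if HBOT does not work, disease progression would be read as HBOT toxicity. The design does not support this. Against a matched SOC group, equal edema rates give an expected difference of zero and only dilute the test.

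Fourth, section 2.3 gives no frequency for edema, and its ventilatory support is broader than the invasive ventilation of 4.2.2. The documents therefore do not show that edema is the usual course or that it will dominate the count.

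Finally, 9.1 defers a formal SAP to the end of the study, so the separation could be made there. That makes the change easy; it does not alter what 9.4.4 now says.

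**Conclusion.** The point holds for the planned pooled comparison. As written, 9.4.4 can net an edema benefit against chamber injuries, and within its four events the direction hypothesized in 9.2 can come true essentially only through edema. Offsetting requires a real edema benefit; without one, the loss is power.

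The size is illustrative, because edema and injury rates are assumed and ventilation rates stand in for edema. The nine-injury break-even is the extreme case, q = 1. What does not depend on q = 1 is the loss of ability to show harm: in every scenario run with 10% injuries, pooling leaves roughly 0 to 23% against about 78% for chamber events alone. This should be corrected before the analysis is fixed.

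**What to change.** Keep acute pulmonary edema in 4.2.3 and 8.1 as a collected event that may be related to HBOT. In 9.4.4:

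1. Analyse acute pulmonary edema on its own line for both groups, with onset relative to the last session in the HBOT group.
2. Report otic barotrauma, myopia and oxygen toxicity seizures as the number and percentage of HBOT patients affected, with an exact 95% interval.
3. State whether the count is this list or all SAEs as defined in 8.3. Section 9.4.4 now applies the label of severe adverse events to a list that 4.2.3 and 8.1 give as possibly related AEs, while 8.3 defines serious events by outcome. A count of all SAEs would bring in more disease progression.
4. Do not use a pooled count to support the 9.2 safety hypothesis.

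The cost is protocol and SAP wording; the events are already to be recorded, and clinical management is unchanged. The downside is that chamber-specific counts will be small and their intervals wide: 4 of 40 gives an exact (Clopper-Pearson) interval of about 2.8% to 23.7%. The report should say so.
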